Logistic regression and classification and regression trees (CART) will be used to develop a predictive model for successful management of early pregnancy failure, which will serve as the basis for a clinical predictive index [66-68]. Our group has used this methodology with success [69,70]. Initially the predictive model will only include biomarkers, and then both biomarkers and epidemiologic and clinical characteristics will be considered in the predictive model. The sensitivity of the predictive index (i.e., proportion of patients with success who are defined as “high chance of success” by the rule) will be of primary interest [71]. The negative predictive value will also be calculated using the derived sensitivity and specificity with the population prevalence of success. This value is also of clinical interest.

For model building, we will enter all biomarkers that will have shown in the bivariate analysis at least borderline associations with the endpoints of interest ($p < 0.20$), as well as interaction terms that are suggested by the results of the explanatory model. Terms will then be removed from the model using a backward elimination procedure, removing factors which cause an insignificant change in the sensitivity of the model. To test the change in sensitivity between models (with and without the variables), we will use McNemar’s test. In particular, we will be comparing the proportion of correctly classified cases of success between models. The rule would involve calculating a score for each person, based on the actual values of the regression coefficients. The goal is to utilize all variables that improve the sensitivity of the model. Unlike the explanatory model, whose goal is to determine which variables are associated with success, the predictive models will be developed in order to determine which combination of variables best predicts the outcome. Additionally, variables and interactions included in the model must be biologically plausible.

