To be useful, a clinical rule must be easily applied. In order to ensure easy understanding and unhindered application, the variables and parameters comprising the predictive score will be simplified with two methods: 1) by recalculating the predictive score using values of the coefficients, rounded to the nearest integer, and 2) by calculating the score simply as the sum of the dichotomous independent variables identified by the model. (It will be necessary, for this approach to recode continuous predictors as dichotomous variables.) This will result in the most parsimonious model. The performance of the new rules will then be compared with that of more complete models using ROC curves. We plan to evaluate potential cutoffs of each marker to optimize our ability to distinguish among successes and failures.

We will also approach our predictive modeling using CART. Candidates that have an individual area under the curve (AUC) > 0.6 will be considered. CART is useful in identifying complex relationships between biomarkers and clinical outcomes. These analyses recursively split observations into two

groups (nodes), t_L and t_R , based on the covariate that maximizes a given split function. In the case of a continuous outcome, a commonly used split function is the reduction in sums of squares error, i.e. the amount of variability explained by the split. The best split is defined to be the one that best predicts the response where the best predictor is defined to be the one that maximizes the split function. All splits of the observations in each of the resulting nodes are then considered and the best split identified. This process is repeated recursively until a stopping rule is achieved (e.g. no further splits exist with greater than 5 observations in each of the resulting nodes). We will employ 10-fold cross-validation to assess the significance of the resulting tree as described in Breiman [72]. The sensitivity and specificity of the CART versus logistic model will be compared using ROC curves, to determine the best predictive rule for management success. CART software will be used to evaluate combinations of biomarkers creating a tree maximizing sensitivity and a tree maximizing specificity. Data will be combined into a three-tiered algorithm to maximize accuracy.

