The prediction rule will be internally validated with a “bootstrap” approach [73-78]. With this approach, a large number of samples are taken from the original data (with replacement) and the predictive accuracy is tested in each of these samples. Sampling with replacement generates a population identical in composition to the observed sample. This method provides a relatively unbiased estimate of the test characteristics of the predictive rule [78].

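### The ROC comparison that chooses between CART and logistic regression is not tied to out-of-sample predictions, so an unpruned tree would look better while predicting worse

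*Combined protocol and SAP*

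**What the plan says.** Section 2 makes the derivation and internal validation of a prediction model the secondary objective. Section 7.2 (Statistical Methods) builds that model in two ways.

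- **Logistic regression.** For candidates, "we will enter all biomarkers that will have shown in the bivariate analysis at least borderline associations with the endpoints of interest", with a threshold of p < 0.20. Backward elimination based on sensitivity follows.
- **CART.** "Candidates that have an individual area under the curve (AUC) > 0.6 will be considered". Splitting continues until a stopping rule is met. The example given is that "no further splits exist with greater than 5 observations in each of the resulting nodes", which means a smallest end node of 6 women.
- **Cross-validation.** "We will employ 10-fold cross-validation to assess the significance of the resulting tree", with a reference to a CART textbook.
- **Choice of rule.** "The sensitivity and specificity of the CART versus logistic model will be compared using ROC curves, to determine the best predictive rule".
- **Validation.** "The prediction rule will be internally validated with a" bootstrap, described in these words: "a large number of samples are taken from the original data (with replacement) and the predictive accuracy is tested in each of these samples".

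Three things are not stated: whether the deciding ROC curves use predictions for the same women on whom the models were fitted, how (or whether) the tree is pruned, and whether the models are refitted in each bootstrap sample. Section 7.2 also plans separate models for each arm.

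**The concern.** A tree split down to nodes of 6 can isolate small pockets of women who happen to share an outcome. A main-effects logistic model with a few coefficients cannot do that to the same extent. An ROC curve drawn on the fitting data therefore rewards the more flexible method for fitting noise, and the gap between the two curves says little about which rule would work for the next patient.

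The choice between methods is made at this step. Validating only the winner afterwards may show that it performs poorly, but it does not bring back the better model that was set aside. The selected rule is meant to become a clinical index for advising individual women, so choosing the weaker model would defeat the purpose of the objective. Failures are also few, which makes overfitting a practical threat.

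**Working it through.** **1. Size of the modelling data set.** The plan states no AUC or other figure for the CART-logistic comparison. Its nearest figure is the sample size in section 7.1. With success rates of 0.70 and 0.85, two-sided α = 0.05 and 80% power (sidedness and power are assumed here):

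n = [1.96·√(2·0.775·0.225) + 0.842·√(0.70·0.30 + 0.85·0.15)]² / 0.15² ≈ 121 per group.

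The continuity correction raises this to 134, the plan's figure. Inflating by 10% gives 134 × 1.10 ≈ 148 or 134 / 0.90 ≈ 149, consistent with 150 per group. Expected failures are 150 × 0.30 = 45 and 150 × 0.15 = 22.5, about 67.5 in 300 women.

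**2. Simulation inputs.** From the plan: n = 300 (or 150 for one arm), the two candidate screens, and the example node size. Assumed, because the plan gives no values: independent normal markers, their number and their strength. The logistic model used main effects without the backward-elimination step. AUC was computed on the fitting data (apparent) and on new women.

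**3. Unpruned tree, smallest node 6, plan's screens, n = 300.**

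| Setting (log-odds ratio 0.5 per SD) | Apparent AUC: tree v logistic | New women: tree v logistic |
|---|---|---|
| A: 10 markers, 3 informative | 0.905 v 0.738 | 0.591 v 0.705 |
| B: 8 markers, 2 informative | 0.88 v 0.70 | 0.57 v 0.66 |

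In setting A the tree loses 0.905 − 0.591 = 0.314 between fitting data and new women; logistic loses 0.738 − 0.705 = 0.033. The tree led in-sample in 100% of runs and was the worse rule in 100%. Over the linear settings tried (n = 150 and 300, 6-15 markers, log-odds ratio 0.25-0.8) it led in-sample in 100% and was worse in 91-100%. A larger node alone is not enough: with at least 30 women per node the tree still led in-sample in 87% (A) and 95% (B) of runs.

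**4. Does the planned resampling correct this?** A further 60 runs of setting A gave:

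| Basis of comparison | Tree | Logistic |
|---|---|---|
| Apparent | 0.904 | 0.741 |
| Bootstrap as worded (no refit) | 0.903 | 0.740 |
| Optimism-corrected bootstrap | 0.750 | 0.703 |
| Out-of-fold, 10 folds, screens repeated in each fold | 0.586 | 0.691 |
| New women | 0.586 | 0.695 |

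Testing a fixed rule in resamples of its own fitting data returns the apparent AUC almost exactly. Even the optimism correction, which the plan does not describe, still prefers the unpruned tree. Out-of-fold predictions recover the right order, and the tree wins in 0% of runs. With no screens, so that both methods see one common candidate set, they give 0.573 v 0.684, against 0.577 v 0.688 on new women. For one arm (n = 150, plan's screens) they give 0.555 v 0.635, with the tree ahead in 7%.

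**5. If the cross-validation is used to prune.** The tree's apparent AUC falls to 0.595 and it leads in-sample in about 7% of runs.

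**6. Role of the screens.** With no screen at all, the unpruned tree still led in 100% of runs (0.941 v 0.742), so the screens do not create its advantage. They do differ in strictness: a marker with true AUC 0.60 passes AUC > 0.6 in about 51-52% of simulated trials and p < 0.20 in about 91-92%.

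**The case against.** The strongest reply is that the plan never commits to an unpruned tree. The node size is only an example, and the cross-validation is attributed to a textbook that is not available here, so it may be intended for pruning. That stands, and it makes the result conditional: on that reading the problem largely goes away. It does not settle the matter, because the stated purpose is significance, pruning is not mentioned, and one unwritten decision reverses which method wins.

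A reader might also infer more than the documents support:

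- **That nothing out-of-sample is planned.** Cross-validation and a bootstrap are both there. The gap is that neither is linked to the comparison and that the bootstrap wording has no refit step.
- **That the tree would win on pure noise.** The AUC > 0.6 screen would seldom let a noise marker through: at least one passes in only about 5% of trials with 5 markers and 11% with 10. Noise-only figures therefore do not describe this plan.
- **That the AUC screen discards markers acting in one arm.** Such a marker (odds ratio 1.65 per SD) passes a pooled screen in about a third of trials. But section 7.2 also plans arm-specific models, and screened within its own arm it passes in about 77%.
- **That losing U-shaped markers is peculiar to CART.** A strong U-shape passes the AUC screen in 3-4% of trials, but a linear test at p < 0.20 in only about 10%. The plan's lowess smoothing gives logistic some route to such markers.

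Linear signals also favour logistic by construction. That is fair, although three settings with a tree-shaped signal gave the same direction: tree ahead in-sample in 100% of runs, worse on new women in 91-99%. Finally, the plan goes on to combine trees into a three-tiered algorithm, so the ROC comparison may not be the last step.

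**Conclusion.** The concern holds in a conditional form. The step that selects the prediction rule is not tied to out-of-sample performance, and the bootstrap as worded would not expose a wrong choice. With an unpruned tree at the example node size, the plan's screens and modest linear signal, the tree appears better by about 0.17-0.18 in AUC and is worse on new women by about 0.09-0.11. The exact values depend on the assumed number and strength of markers. The direction was the same in every setting with signal, provided the tree was not pruned.

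The differing screens are a separate, lesser defect: they make the comparison not like for like, but they are not why the tree wins. Nothing here touches the primary comparison of success rates between arms.

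**What to change.** In the CART part of section 7.2:

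- state that the tree is pruned by cross-validation, and give the rule;
- give CART and logistic the same prespecified candidate list;
- compare them on out-of-fold predictions from the same 10 folds, with screening, elimination and pruning repeated inside each fold;
- choose the rule on that cross-validated performance.

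In the validation paragraph, describe the bootstrap as repeating the whole procedure, including the choice between methods, in each resample and testing the result on women not drawn into it. Copies of one woman within a resample should stay in the same fold, or the inner cross-validation will leak.

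The cost is revised wording and modest programming. Reported AUCs will be lower, because they will no longer include the gain from fitting noise. No extra participants or data are needed.

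### Section 7.2: the bootstrap as described tests the prediction rule on the data that built it, so it returns the apparent accuracy and removes no optimism

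*Combined protocol and SAP*

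**What the plan says.** Section 2 makes it a secondary objective to derive a prediction model, validate it internally and use it in counselling and treatment choice. Section 7.2 builds the logistic rule in several data-driven steps:

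- a bivariate screen at p < 0.20;
- backward elimination by McNemar's test, "removing factors which cause an insignificant change in the sensitivity of the model";
- a search for marker cut-offs;
- simplification, by rounding coefficients or by adding up dichotomised predictors.

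There is a model for all women and one for each arm. A CART tree is grown in parallel from its own list of markers: "Candidates that have an individual area under the curve (AUC) > 0.6 will be considered".

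The paragraph on internal validation, just before Section 7.3, gives the method in one clause: "a large number of samples are taken from the original data (with replacement) and the predictive accuracy is tested in each of these samples". It then claims: "This method provides a relatively unbiased estimate of the test characteristics of the predictive rule". References 73-78 are cited. The only other resampling is for the tree: "We will employ 10-fold cross-validation to assess the significance of the resulting tree". The accuracy figures also have a further use: "The negative predictive value will also be calculated using the derived sensitivity and specificity with the population prevalence of success".

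**The concern.** A rule that has been screened, pruned, given cut-offs and rounded on one data set looks better in that data set than it will in new women. Internal validation exists to estimate that gap and remove it. A bootstrap does so only if the rule is rebuilt in each sample and its performance there is compared with its performance on data that did not build it. The validation paragraph states neither step, yet claims little bias.

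At stake is how far the published rule can be trusted for individual counselling. Overstated specificity and negative predictive value would make the rule seem better than it is at identifying women in whom medical treatment will fail. The treatment comparison does not depend on any of this.

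**Working it through.** The plan gives no accuracy or optimism figure to reproduce, so the check is what the described procedure estimates, and by how much that misses.

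**1. What the literal procedure returns.** Let D be the trial data, r the finished rule and D* a bootstrap sample. Given the numbers of successes and failures in D* (at least one of each), its successes are uniform draws from the successes in D, and its failures uniform draws from the failures in D. Hence the expected sensitivity of r in D* equals its sensitivity in D, and likewise for specificity. Each success-failure pair in D* is a uniform draw from the pairs in D, so the expected AUC in D* equals the AUC in D. More samples only bring the average closer to the apparent value. In simulation the two agreed within 0.002.

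An optimism-corrected bootstrap is different. With r_b rebuilt in sample D*_b:

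corrected AUC = apparent AUC − mean over b of [AUC of r_b in D*_b − AUC of r_b in D].

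Rebuilding but testing in the same sample does not help. With 5, 10 and 20 noise markers and 300 women it gave AUC 0.602, 0.653 and 0.713, against apparent values of 0.560, 0.594 and 0.634 and a true value of 0.50.

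**2. Inputs.** From Section 7.1: 300 women, 150 per arm, success 70% and 85%. The mean is (70 + 85)/2 = 77.5%. Expected failures are 150 × 0.30 + 150 × 0.15 = 45 + 22.5 = 67.5. From Section 7.2: the p < 0.20 screen and a logistic fit. Assumed: independent normal markers, their number and strength, and a Youden cut-off for sensitivity and specificity.

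**3. AUC after screen and logistic fit, before elimination.**

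| Scenario | As written | True | Excess |
|---|---|---|---|
| 10 noise markers, n=300, 77.5% success | 0.585 | 0.499 | 0.086 |
| 10 noise markers, n=150, 85% success | 0.641 | 0.502 | 0.139 |
| 2 weak (log-odds 0.5, 0.3) among 10, n=300 | 0.676 | 0.631 | 0.045 |
| 2 strong (log-odds 1.0, 0.7) among 5, n=300 | 0.791 | 0.774 | 0.017 |

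With rebuilding and subtraction, the estimate was generally within about 0.03 of the truth. One separate run (10 noise markers, n=150, 70% success) was further off: 0.632 as written, 0.543 corrected, 0.500 true.

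**4. Sensitivity and specificity at the Youden cut-off (as written / true; apparent values in the last row).**

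| Scenario | Sensitivity | Specificity |
|---|---|---|
| Noise, n=300 | 62 / 58% | 55 / 42% |
| Noise, n=150, 85% success | 71 / 66% | 58 / 34% |
| Weak, n=300 | 64 / 61% | 66 / 57% |
| Strong, n=300 | 72 / 70% | 75 / 69% |

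Sensitivity is 2 to 5 points too high and specificity 6 to 24. With 10 noise markers none passes the screen in 0.8^10 = 0.107 of data sets, and the noise rows appear to count these as 100% sensitivity and 0% specificity. Without them a separate n=300 run gave as-written values of 59% and 62%.

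**5. Negative predictive value, weak markers.** NPV = spec × 0.225 / [spec × 0.225 + (1 − sens) × 0.775].

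- As written: 0.664 × 0.225 / (0.664 × 0.225 + 0.358 × 0.775) = 0.1494 / 0.4269 = 0.35.
- True: 0.568 × 0.225 / (0.568 × 0.225 + 0.391 × 0.775) = 0.1278 / 0.4308 = 0.30.
- Corrected: 0.576 × 0.225 / (0.576 × 0.225 + 0.386 × 0.775) = 0.1296 / 0.4288 = 0.30.

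The base failure rate is 22.5%, so the apparent gain over base is 12.5 points where the true gain is about 7.5.

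**6. After elimination.** With McNemar's test at 0.05 and several probability cut-offs (all assumed), noise markers gave as-written AUCs of 0.50 to 0.57 at n=300 and 0.50 to 0.61 at n=150. Weak markers gave an excess of 0.02 to 0.03, and zero where elimination emptied the model.

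**The case against.** The strongest reply is that this is brevity, not error. The paragraph never says the rule is held fixed, and its references include work on the bias of the apparent error rate and on the bootstrap and cross-validation. A corrected bootstrap may well be intended. That stands as to intent, and a reader should not infer that the analysts are bound to report uncorrected figures. It does not rescue the text: several variants exist, and the one put into words lacks the property claimed for it.

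Second, the effect can be small. Section 7.2 names sensitivity as the measure of primary interest, and it moves by only a few points. Section 1.2 reports preliminary associations for βhCG and Activin, so pure noise is pessimistic; with two strong markers the AUC excess is about 0.02. This stands, and it limits the size.

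Third, cross-validation is already planned. It is, but for the CART tree only.

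Fourth, not every building step can be rerun by program. Lowess shapes, biological plausibility and suggested interactions involve judgement. This stands and is allowed for in the fix.

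A reader might also infer that the elimination step has no stated direction, or that it will wreck the logistic rule. The documents do not support either. The removal criterion is non-directional, but the same paragraph gives the aim of keeping variables that improve sensitivity. The probability cut-off is missing, yet the planned ROC comparison of logistic and CART rules would partly expose a poor logistic model. Nor should one infer that any cut-off above the success rate is harmless: in the strong-marker simulation (n=300) at 0.80, keeping only terms whose removal significantly lowers sensitivity took the true AUC from 0.78 to 0.72.

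**Conclusion.** The point holds for the secondary prediction objective. Followed literally, the bootstrap in Section 7.2 reports apparent accuracy, and the claim of near-unbiasedness does not follow from the procedure described. This rests on the algebra in step 1 and needs no assumption about markers.

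The size does need assumptions. Before elimination the AUC excess runs from about 0.02 (strong markers, n=300) to about 0.14 (noise, n=150, 85% success). Specificity and negative predictive value carry more of the inflation than sensitivity. The per-arm models are more exposed because they have fewer failures: 22.5 are expected in the combination arm. Elimination reduces the excess by an amount that depends on a cut-off the plan does not give. Clinical predictors, interactions, rounding and CART were not simulated. This should be corrected before the prediction analysis, but it does not bear on the primary result.

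**What to change.** State in the internal-validation paragraph of Section 7.2 that:

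- every building step that can be programmed (screening, elimination, cut-off choice, rounding, CART) is repeated in each bootstrap sample;
- each resulting rule is tested on the original data;
- the mean optimism is subtracted from the apparent AUC, sensitivity and specificity, for the overall and the per-arm models;
- the negative predictive value is computed from the corrected figures;
- steps done by judgement are not repeated, so some optimism may remain, and the report will say so.

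The cost is wording, programming and computing time, and less favourable reported accuracy. No further data are needed.

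A minor clarification, separate from the main point: elimination rests on a comparison in which "we will be comparing the proportion of correctly classified cases of success between models". The model-building paragraph should give the probability cut-off (or minimum specificity) at which that comparison is made, and should align the non-directional removal criterion with the stated aim of keeping variables that improve sensitivity.

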7.3. Subject Population(s) for Analysis

All-randomized population will be subject to analysis.

7.4. Interim Analysis

Since safety and failure is a consideration in this study, we have chosen to use a group sequential design. Thus, in addition to the final analysis, we are planning on performing an interim statistical analysis during the course of the study. The purpose of the interim analyses will be to determine whether or not there is sufficient evidence of an increased failure rate in the combined arm compared to the control such that the trial should be discontinued prior to reaching the target accrual goal. The interim analysis will be performed after approximately 1/2 (150 subjects) of the total required patients have completed their primary outcome. This interim analysis will also examine whether or not there is sufficient evidence of an increased infection rate in the combined arm.

The primary outcome for the interim analyses will be the comparison of success/failure rates between the treatment arms. This comparison will be accomplished by means of a simple logistic regression model for the outcomes versus treatment. An approximate O’Brien-Fleming boundary will be used at the interim look to calculate the nominal significance level to which interim p-values are compared (O’Brien PC 1979). Using the O’Brien Fleming spending function, the two analyses (interim + final) should use the following incremental α values (0.003, 0.047) in order to achieve an overall $\alpha=0.05$.

Stopping criteria are for:

(1) **Clear superiority** -- whether the misoprostol alone is clearly inferior to combined treatment. For these calculations, we trade off the power to detect a difference and the size of that difference. Assuming $\alpha=0.003$ for boundaries for the interim analysis when 150 women have been followed to completion power is limited except to detect large reductions in failure rates. For example, power is approximately 0.80 to detect a reduction from 30% in the misoprostol alone arm to 6.7% in the

combination arm. Thus, early or premature stopping for superiority is unlikely, without dramatic improvement from the combined treatment.

(2) **Inferiority.** Power is limited to identify inferiority of the combined treatment, with 0.8 power to demonstrate a 30%-point increase in the risk of failure from 30% in the misoprostol alone arm to 60.7% in the combined treatment arm. Instead, we will base inferiority on the safety concern (see (4)) of an increased failure rate in the combination arm.

